2.2 Analysis sets

The **Full Analysis Set** (FAS) comprises all randomized participants. According to the intent-to-treat principle, participants will be analyzed according to the treatment group they have been assigned to during the randomization procedure.

The **Per-Protocol Set** is a subset of the FAS in which participants are not treated with any incilisiran if they are randomized to the usual care treatment group, and do not have any major protocol deviations (including deviations from inclusion/exclusion criteria) in either treatment group.

The **Restricted Set 1** is a subset of the FAS which includes only participants without changes in background lipid-lowering therapy. A change includes starting a new lipid-lowering therapy or stopping an existing lipid-lowering therapy after the study treatment start date.

The **Restricted Set 2** is a subset of the FAS which includes only participants who received three doses of inclisiran in the “inclisiran first” implementation strategy group (i.e., excludes patients in the “inclisiran first” implementation strategy group who missed one or more doses) and all participants in the usual care group.

The **Safety Set** includes all participants who received study treatment. Participants will be analyzed according to the study treatment received. Refer to Table 2-1 for assignment of actual treatment for the different scenarios. Participants in the usual care treatment group who have data collected at the baseline visit will be included in the Safety Set.

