## 8 Visit schedule and assessments

The Assessment Schedule ([Table 8-1](#)) lists the assessments when they are performed. All data obtained from these assessments must be supported in the participant’s source documentation.

Participants should be seen for all visits/assessments as outlined in the assessment schedule ([Table 8-1](#)) or as close to the designated day/time as possible (+/- 7 days). Missed or rescheduled visits should not lead to automatic discontinuation. Participants may be seen at

any time for an unscheduled visit, e.g., if they experience deterioration or AEs that in the opinion of the Investigator/qualified site staff requires closer monitoring.

Participants who discontinue from study treatment should continue to attend the remaining study visits as indicated in the Assessment Schedule ([Table 8-1](#)).

Participants who discontinue from study or withdraw their consent should be scheduled for a final evaluation visit if they agree, as soon as possible, at which time all of the assessments listed for the final visit will be performed. At this final visit, all investigational product should be reconciled, and the adverse event and concomitant medications not previously reported must be recorded on the eCRF.

Participants will have to comply with the following restrictions during the study:

- Participants need to fast for at least 8 hours for all visits (measurement of lipids/lipoproteins and blood glucose requires participants to be fasting). If the participant has not fasted, the collection of laboratory evaluations must be rescheduled.
- Blood donation will not be allowed at any time during the study

The “X” in the table denotes the assessments to be recorded in the clinical database or received electronically from a vendor. The “S” in the table denotes the assessments that are only in the participant’s source documentation and do not need to be recorded in the clinical database.

As per [Section 4.6](#), during a Public Health Emergency that limits or prevents on-site study visits, alternative methods of providing continuing care may be implemented by the Investigator as the situation dictates. If allowable by a local Health Authority and depending on operational capabilities, phone calls, virtual contacts (e.g. tele consult) or visits by site staff/ home nursing staff to the participant’s home, can replace on-site study visits, for the duration of the disruption until it is safe for the participant to visit the site again.

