#### **12.4.7 Supportive analyses**

The primary analysis of the two primary efficacy variables will be repeated for the Per-Protocol Set, Restricted Set 1, and Restricted Set 2.

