Since inclisiran is commercially available in the US as of late-2021, utilization of it in the usual care group at the sole discretion of the treating physician will not be encouraged, but will also not be prohibited to avoid withholding of appropriate care. If treatment with a PCSK9-inhibiting monoclonal antibody was initiated and a patient would have to be transitioned to inclisiran, the PCSK9-inhibiting monoclonal antibody should be discontinued.

The collection of data from trial sites through eCRFs will be complemented with EHR data and claims data (e.g., lipid measurements and concomitant medications).

Participants randomized to "inclisiran first" implementation strategy group will receive inclisiran at Day 0, Day 90 and Day 270, consistent with the dosing regimen studied in the Phase III trials.

While study visits will be preferentially performed in-person at the study sites, phone or virtual visits are an acceptable alternative if in-person visits are not permitted or impractical due to a Public Health Emergency. Site or home health nursing service may be used to assist with blood draws and/or study medication administration if required at these visits. Informed consent forms will be available in English and Spanish.

Figure 1-1 Study Design

Additional important considerations of the study design include:

Recruitment: Potentially eligible participants will be pre-screened using EHR, claims and/or laboratory databases. This will maximize the representativeness of the sample because it will reduce selection bias that occurs when investigators identify all participants by convenience sampling. Moreover, centrally identifying potential study sites and participants using EHR, claims and/or laboratory data will allow us to ensure that the study sites are representative while excluding sites that manage lipids more aggressively than is typical (for example specialized lipid clinics). Eligible participants will need to consent to having health records made available as part of the collection of medical and pharmacy claims. Several tactics will aim to enhance inclusion of minority and medically underserved populations, as these populations are traditionally underrepresented in clinical trials.

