2.3.1 Patient disposition

Participant disposition will be summarized as follows:

- The number of participants who signed the informed consent form, are screen failures, are randomized, are treated (Safety Set), completed the study or who discontinued early along with reasons for early study discontinuation, the number of screened subjects, completed screening phase and were randomized, completed screening phase but were not randomized, did not complete screening phase, and primary reason for not completing screening phase will be summarized for all screened participants.
- The number of participants in each analysis population along with reasons for exclusion from each analysis population will be summarized by treatment group for all randomized participants.
- The number of participants who completed the study or who discontinued early along with reasons for early study discontinuation will be summarized by treatment group for the FAS.
- The duration on study (number of days from study start date to study end date [last recorded contact/participation date in the database]) will be summarized by treatment for the FAS.

A summary of failed inclusion/exclusion criteria will be provided for all screened participants and by treatment group for the FAS.

A summary of the number of participants by visit will be provided by treatment group for the FAS.

The number and percentage of participants with important protocol deviations will be summarized by treatment group for the FAS.

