2.5.1 Primary endpoint(s)

The primary efficacy variables are the following:

1. Percent change from baseline in LDL-C
2. Discontinuation of statin therapy (i.e., no statin use \geq 30 days before the end-of-study visit) (yes, no)

The primary analysis time point for both primary efficacy variables is at Day 330.

The following provides additional details on the derivation of primary efficacy variable 2.

If a participant is considered a study completer and has a non-missing visit date for the nominal Day 330 visit recorded, a statin assessment date (to assess if the participant was taking statins at this point in time) will be calculated by subtracting 30 days from the Day 330 visit date (e.g., study Day 300 if the participant completes on study Day 330). The statin assessment date will be compared to the maximum statin end date of all statin medications taken by the participant. If the last statin is recorded as ongoing at study end date, the maximum statin end date will be set to the study end date.

- If the participant was on a statin on or after this statin assessment day (maximum statin end date \geq statin assessment date), the participant will be considered as discontinued statin = 'no.'
- If the participant was not on a statin on and after this statin assessment day (maximum statin end date $<$ statin assessment date), or they were a completer who did not have a Day 330 visit, the participant will be considered as discontinued statin = 'yes.'

All early termination participants will be considered to not be on a statin for this endpoint (the participant will be considered as discontinued statin = 'yes').

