For primary efficacy variable 2, a one-sided 98.75% confidence interval for treatment difference ("inclisiran first" implementation strategy – usual care) in the proportion of participants who discontinued statin therapy at Day 330 will be computed using the normal approximation to the binomial distribution. Non-inferiority of the "inclisiran first" implementation strategy to usual care will be declared if the upper limit of the confidence interval does not exceed the non-inferiority margin of 0.15. The difference in proportions and associated two-sided 97.5% confidence interval will also be provided.

The primary analysis of primary efficacy variable 2 will be based on the FAS excluding participants who had medical history of statin intolerance. The primary analysis of this variable will be repeated for the Per-Protocol Set and Restricted Set 2.

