For primary efficacy variable 2, i.e., discontinuation of statin therapy (yes, no), a z-test for a non-inferiority test of two proportions, an allocation ratio of 1:1, and a one-sided significance level of 0.0125 were used in the calculation of sample size. Table 3-2 considers total sample sizes for 0.20 and 0.25 as the true proportions of participants who discontinue statin therapy in each treatment group, and non-inferiority margins of 0.10 and 0.15 for the "inclisiran first" implementation group to be no worse than the usual care group (nQuery Version 8.4.1.0). From Table 3-2, a true proportion of 0.20 for participants who discontinue statin therapy in each treatment group by Day 330, a non-inferiority margin of 0.15, and a power of 0.90 were chosen to provide a total sample size of 354 participants.

Table 3-2 Sample Size Calculations for Statin Statin Therapy Discontinuation

Proportion in usual care group	Non-inferiority margin	Power = 0.85	Power = 0.90
0.20	0.10	688	796
0.20	0.15	306	354
0.25	0.10	806	932
0.25	0.15	360	414

Based on the sample size calculations in Table 3-1 and Table 3-2, a total sample size of 354 together with a loss to follow-up rate of 10% at Day 330 and a statin intolerance rate at baseline of 10% (i.e., a total of 20% due to loss to follow-up and statin intolerance at baseline) require

approximately 444 participants (222 participants per treatment group) to be randomized. This will also allow examination of subgroups with reasonable sample sizes.

4 Change to protocol specified analyses

Changes from Protocol version 01 (amended protocol) include the following:

1. Protocol Section 12.4.2 states that an unstructured working correlation matrix will be assumed for the MMRM. An unstructured covariance matrix will be used instead.
2. The protocol uses Day 0 as the first inclisiran dose day. In order to aid in counting of dosing days the first dose day will be referred to as Day 1.

Changes from Protocol version 02 (amended protocol) include the following:

3. Protocol Section 12 notes that the interquartile range will be provided. In order to streamline the tables this statistic was removed.
4. Protocol Section 12.2 notes that relevant medical histories and current medical conditions at baseline would be summarized using the Safety Set, the FAS was used instead.

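### Restricted Set 2 removes inclisiran-first early leavers (all coded as statin stoppers) but keeps usual-care ones, which tilts the supportive repeat of the statin-discontinuation test toward non-inferiority

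*SAP*

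**What the plan says.** - **The set.** SAP 2.2 and Table 5-1 restrict the inclisiran-first arm to participants with three doses and place no condition on usual care. The SAP 2.2 definition sets the excluded members of the inclisiran-first "implementation strategy group who missed one or more doses) and all participants in the usual care group" side by side, the second group being kept in full.
- **Dose days.** Inclisiran-first participants "will receive inclisiran at Day 0, Day 90 and Day 270" (SAP 1.1), so three doses means reaching Day 270 of 330.
- **Coding of leavers.** SAP 2.5.1: "All early termination participants will be considered to not be on a statin for this endpoint". This applies in both arms.
- **The repeat.** For the statin variable, SAP 2.5.2 states: "The primary analysis of this variable will be repeated for the Per-Protocol Set and Restricted Set 2". Protocol 12.4.7 is wider: "The primary analysis of the two primary efficacy variables will be repeated for the Per-Protocol Set, Restricted Set 1, and Restricted Set 2".
- **Missed doses without leaving.** Protocol section 8: "Participants who discontinue from study treatment should continue to attend the remaining study visits". Some completers may therefore have fewer than three doses.
- **Reporting.** SAP 2.3.1: "The number of participants in each analysis population along with reasons for exclusion from each analysis population will be summarized by treatment group".
- **Planned loss.** SAP section 3 uses "a total sample size of 354 together with a loss to follow-up rate of 10% at Day 330".

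The decision analysis for this variable is the FAS without participants who have a history of statin intolerance.

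**The concern.** For this endpoint, leaving the study is itself counted as the unfavourable outcome. A set that selects on completing three doses therefore selects on the outcome, and it does so in one arm only. Inclisiran-first participants who leave before dose 3 are all stoppers by rule, and all are removed. Their usual-care counterparts are also stoppers by rule, and all stay. (Those who leave after dose 3 stay in both arms.) Nothing in the SAP matches usual care to this selection or warns about its direction.

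At stake is how the supportive table can be read. If most of those removed are early leavers, agreement with the FAS says little, because the way the set is built makes disagreement very unlikely.

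**Working it through.** **Inputs from the plan.** Rate 0.20 per arm, margin 0.15, one-sided alpha 0.0125, power 0.90, loss 10%, statin intolerance 10%, 222 randomized per arm (SAP section 3); dose 3 at Day 270 (SAP 1.1). The rule is difference + 2.2414 × unpooled SE ≤ 0.15.

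**The plan's own figure.** n per arm = (2.2414 + 1.2816)² × 2 × 0.20 × 0.80 / 0.15², which rounds up to 177, so 354 in total, as in SAP Table 3-2. Then 177/0.80 rounds up to 222 per arm, or 444.

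**Assumptions.** 200 per arm (222 less 10%); equal loss in both arms; exits spread evenly, so the share leaving before dose 3 is e = 0.10 × 270/330 = 0.0818; and 0.20 is the FAS rate with leavers already counted as stoppers.

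**Shift in the difference.** Let p be the FAS rate, m the share of the arm who complete but missed a dose, and q their stopping rate. The Restricted Set 2 rate in inclisiran-first is (p − e − mq)/(1 − e − m). Usual care is unchanged. With p = 0.20 in both arms and q = 0:

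| Loss before dose 3 (e) | m | Shift |
|---|---|---|
| 0.0818 (10% loss, even) | 0 | -0.071 |
| 0.0409 (5% loss, even) | 0 | -0.034 |
| 0.05 (10% loss, half before dose 3) | 0 | -0.042 |
| 0.10 (10% loss, all before dose 3) | 0 | -0.089 |
| 0.0818 | 0.05 | -0.064 |
| 0.0818 | 0.10 | -0.056 |
| 0.0818 | 0.20 | -0.035 |

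With q = 0 the shift reaches zero at m = e(1 − p)/p: 0.33 for p = 0.20, 0.19 for p = 0.30 and 0.15 for p = 0.35.

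**Worked counts** (200 × 0.0818 ≈ 16 leavers before dose 3):

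| Analysis | Counts | Difference | Upper limit |
|---|---|---|---|
| FAS | 40/200 v 40/200 | 0 | 0.090 |
| Restricted Set 2 as written | 24/184 v 40/200 | -0.070 | 0.015 |
| Same leavers removed from both arms | 24/184 v 24/184 | 0 | 0.079 |

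With 40/200 in usual care, the largest passing inclisiran-first count is 51 on the FAS. On Restricted Set 2 it is 62, counted before the 16 are removed.

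**Can it disagree with a FAS pass?** With m = 0, an enumeration over inclisiran-first stopper counts of 1 to 100 out of 200, with up to 40 stoppers removed, covered 489,446 removals from a FAS pass. The upper limit fell in every one and none became a fail.

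**Simulation** (1.5 million trials per case, e = 0.0818 in both arms, m = 0). In the last column the margin is 0.15/(1 − 0.0818) = 0.163.

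| True FAS rates | FAS passes | Restricted Set 2 agrees, given FAS pass | Both-arm removal agrees, margin 0.15 | Both-arm removal agrees, margin rescaled |
|---|---|---|---|---|
| 0.30 v 0.20 | 14% | 100% | 59% | 78% |
| 0.35 v 0.20 | 1.3% | 100% | 29% | 51% |

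At 0.35 v 0.20, Restricted Set 2 passes in about 18% of all trials.

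**Completers who missed a dose.** If all of them kept the statin, agreement at 0.30 and 0.35 v 0.20 is 99% and 94% for m = 0.10, and 60% and 24% for m = 0.20. If missed doses are unrelated to statin use, agreement with m = 0.20 is still 99.8% and 99.4%.

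**Alternative reading of 0.20.** If 0.20 is the rate among completers, 10% loss gives a FAS rate of 0.28. The equal-arms shift is then -0.063. At a true FAS difference of 0.15, Restricted Set 2 passes in about 12% of trials against about 1.2% for the FAS (about 5% at 5% loss, 23% at 15% loss).

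**The case against.** **It is only supportive, and openly one-sided.** Usual care has no study doses, so a full-dosing set must be one-sided, and both documents say that it is. No passage assigns the repeat a robustness role, and no success rule attaches to it. This stands. A reader might infer that the trial's non-inferiority claim or its error rate is compromised. The documents do not support that, because success is declared on the FAS alone. The 18% describes a supportive table and is not a false-positive rate for the trial. What remains is that full dosing suits LDL-C better than an endpoint where leaving counts as the event.

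**The both-arm comparator is too strict.** Removing leavers from both arms divides the true difference by 0.918, so 0.15 becomes 0.163 while the margin stays at 0.15. This is correct. The fair contrast at the margin lies between 29% and 51%, against 100%.

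**0.30 v 0.20 is not an error.** Correct: a true difference of 0.10 lies inside the margin, so a pass there is right. Only 0.35 v 0.20 illustrates a false pass.

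**The removed stoppers are visible.** Largely correct. Counts by arm are planned for both sets, so subtracting the inclisiran-first rows gives the number (40/200 to 24/184 is 16 removed, all stoppers). It would be wrong to infer that the SAP hides it.

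**Dose-missing completers could cancel the effect.** They could, but only if they are numerous and mostly still on a statin. The documents give no rate for them.

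**Conclusion.** The point holds as a minor one. The Restricted Set 2 repeat of the statin-discontinuation test is biased toward non-inferiority whenever the share coded as stoppers among those removed exceeds the arm's FAS rate. With equal FAS rates of 0.20 the shift is about -0.07 at the planned 10% loss spread evenly, and about -0.03 at 5% loss. With no dose-missing completers the repeat cannot contradict a FAS pass, including a false one.

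The bias fades only if roughly 15 to 20% or more of the arm, at the higher stopping rates, are completers who missed a dose but stayed on a statin. It persists if missed doses are unrelated to statin use. Exit timing, equal loss and the number of such completers are assumptions. A reader might take the 100% agreement as unconditional; it is not, because it needs nearly all of those removed to be early leavers or other stoppers. The FAS decision and its type I error are untouched.

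**What to change.** In SAP 2.5.2, omit Restricted Set 2 for primary efficacy variable 2, as that section already does for Restricted Set 1.

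Alternatively, keep it but require usual-care participants to be still in the study at the Day 270 visit for this repeat. State that the match is approximate, because inclisiran-first completers who missed a dose stay excluded, and that the removal slightly enlarges the difference relative to the 0.15 margin.

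Either way, record the change in SAP section 4, because Protocol 12.4.7 lists the set for both primary variables. A separate count of removed stoppers is optional, since it follows by subtraction from planned tables.

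The cost is one line in SAP 2.5.2 and one entry in section 4 before database lock, with no new data. The downside is that one protocol-listed supportive table is dropped or redefined.

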### **12.1 Analysis sets**

The Full Analysis Set (FAS) comprises all randomized participants. According to the intent-to-treat principle, participants will be analyzed according to the treatment group they have been assigned to during the randomization procedure.

The Per-Protocol Set is a subset of the Full Analysis Set in which participants are not treated with any inclisiran if they are randomized to the usual care treatment group or do not have any major protocol deviations (including deviations from inclusion/exclusion criteria) in either treatment group.

The Restricted Set 1 is a subset of the Full Analysis Set, which includes only participants without changes in background lipid-lowering therapy.

The Restricted Set 2 is a subset of the Full Analysis Set, which includes only participants who received three doses of inclisiran in the “inclisiran first” implementation strategy group (i.e., excludes patients in the “inclisiran first” implementation strategy group who missed one or more doses) and all participants in the usual care group (including participants who may have used commercially available inclisiran).

The Safety Set includes all participants who received study treatment. Participants will be analyzed according to the study treatment received at randomization.

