2.1.1 General definitions

Study Treatment

The following are the investigational treatments:

- Inclisiran (KJX839), 284 mg, 1.5 ml liquid in a single-use prefilled syringe (PFS) for s.c. administration plus usual care
- Usual care alone

The following treatment labels will be used for all tables, listings and figures:

- Inclisiran First
- Usual Care

Study treatment start and end date

Study treatment start date is defined as the first date when a non-zero dose of study drug is administered for the inclisiran group. If a participant, who is randomized to the Inclisiran First group, does not take any study drug then treatment start date will be the randomization date.

For the usual care alone group the study treatment start date will be the randomization date.

“Day 1” will be used to identify study treatment start date for both treatments.

Study treatment end date is defined as the treatment phase completion date recorded on the “Treatment Disposition” CRF for inclisiran participants. For the usual care alone group, the study treatment end date is the last recorded contact/participation date in the database.

Study start and end date

Study start date is defined as the first date when a non-zero dose of study drug is administered for the inclisiran group. If a participant, who is randomized to the Inclisiran First group, does not take any study drug then study start date will be the randomization date.

For the usual care alone group the study start date will be the randomization date.

Study end date is defined as the date of last recorded contact/participation date in the database.

Planned and actual treatment definitions

Table 2-1 Planned and Actual Treatment Definitions

Randomized Treatment Group	Inclisiran Use Scenario During Study (Inclisiran Use Recorded as Study Treatment or Concomitant Medication)	Planned Treatment	Actual Treatment
Inclisiran First	Received at least one dose of inclisiran	Inclisiran First	Inclisiran First
Inclisiran First	Never received inclisiran	Inclisiran First	Usual Care
Usual Care	Received at least one dose of inclisiran	Usual Care	Inclisiran First
Usual Care	Never received inclisiran	Usual Care	Usual Care

Study day

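### The SAP counts a usual-care participant's safety events under Inclisiran First even when they precede the first inclisiran dose, and its list of protocol changes omits this regrouping

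*SAP*

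**What the plan says.** Protocol section 12.1 defines the Safety Set grouping as follows: "Participants will be analyzed according to the study treatment received at randomization".

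SAP section 2.2 replaces this with: "Participants will be analyzed according to the study treatment received. Refer to Table 2-1 for assignment of actual treatment for the different scenarios". SAP Table 2-1 (section 2.1.1) takes use from either source: "Inclisiran Use Recorded as Study Treatment or Concomitant Medication". A participant randomized to usual care who meets the condition "Received at least one dose of inclisiran" has actual treatment Inclisiran First. Each participant carries one label for the whole study.

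The clock is also set in SAP section 2.1.1. For the inclisiran arm: "Study treatment start date is defined as the first date when a non-zero dose of study drug is administered for the inclisiran group". For the other arm: "For the usual care alone group the study treatment start date will be the randomization date". In both arms, study days are then counted with that date as Day 1.

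SAP section 2.7 runs all safety analyses on the Safety Set. Section 2.7.1 judges treatment emergence against Day 1 and plans risk ratios with 95% confidence intervals for common events, serious events and events leading to withdrawal of study treatment. The shift tables in section 2.7.3 use the worst post-baseline value.

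**The concern.** Commercial inclisiran is not prohibited in the usual-care arm, and SAP Table 2-1 has a row for it, so the case is foreseen. A usual-care participant may have months of follow-up before a first inclisiran dose. Under the SAP, an adverse event or abnormal laboratory value from those months sits in the Inclisiran First column, although the participant had received no inclisiran.

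The safety and tolerability of inclisiran is a stated secondary objective. Unexposed time in the inclisiran column pulls a real difference toward no difference, and individual events are credited to a drug not yet given. The SAP plans no as-randomized safety table against which a reader could check this. The regrouping also departs from the protocol without being declared.

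**Working it through.** **Text check.** The protocol phrase could mean the treatment assigned at randomization or the treatment given at that visit. On either reading, a later commercial dose leaves the participant in usual care, so the SAP rule differs. SAP section 4 lists six changes: the covariance matrix, Day 0 versus Day 1 labelling, the interquartile range, the analysis set for medical history, secondary variable 22, and the scope of listings. None concerns the grouping of the Safety Set. No passage splits or censors safety follow-up at the first inclisiran dose.

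**Inputs.** From the documents: N = 222 per arm and T = 330 days. Assumed, because the documents give no crossover rate or timing: k = 4, 11 or 22 crossovers (2%, 5% or 10% of 222), first inclisiran dose at day d = 180, usual-care risk 0.15 over 330 days, true rate ratio R = 2, and crossovers of average risk.

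**Unexposed share of Inclisiran First person-time**, k × d / ((N + k) × T):
- k = 4: 720 / 74,580 = 1.0%
- k = 11: 1,980 / 76,890 = 2.6%
- k = 22: 3,960 / 80,520 = 4.9%

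**Expected crossovers with a pre-dose event**, k × (1 − 0.85^(180/330)) = k × 0.0848: 0.3, 0.9 and 1.9.

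**Effect on the planned risk ratio.**
- Risk if exposed throughout: 1 − 0.85² = 0.2775. True risk ratio: 0.2775 / 0.15 = 1.85.
- Crossover's exposure-weighted exponent: (180 + 150 × 2) / 330 = 1.4545. Crossover's risk: 1 − 0.85^1.4545 = 0.2105.
- SAP Table 2-1: [(222 × 0.2775 + k × 0.2105) / (222 + k)] / 0.15.
- As randomized: 0.2775 / [((222 − k) × 0.15 + k × 0.2105) / 222].

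| k | SAP Table 2-1 | As randomized |
|---|---|---|
| 4 | 1.84 | 1.84 |
| 11 | 1.83 | 1.81 |
| 22 | 1.81 | 1.78 |

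**Same check per person-time.** With usual-care rate 1, the Table 2-1 rate ratio is (222 × 2 + k × 1.4545) / (222 + k) = 1.99, 1.97 and 1.95. Splitting each crossover's time at the first dose returns 2.00.

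**Sampling error for scale.** The standard error of the log risk ratio at 1.85 is √(0.7225/61.605 + 0.85/33.3) = 0.193. The 95% interval is 1.85 × exp(±1.96 × 0.193), or about 1.27 to 2.70.

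**The case against.** Giving each participant one actual-treatment label is an ordinary way to form a safety set, and SAP Table 2-1 states it openly. On the figures above it dilutes slightly less than the protocol's own grouping. The protocol (section 4.1.1) expects inclisiran use in the comparator arm to be minimal, and the shifts of 0.01 to 0.04 are far inside sampling error. Inclisiran cannot cause an injection-site event before its first dose, and pre-dose events should seldom be judged related to study treatment. Listings and medication dates let a reader trace the order. A split needs a person-time analysis that the SAP does not otherwise use. All of this stands, and it is why the point is minor.

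Two parts of the defence are weaker. SAP section 4 introduces its items with the word include, so it may not be exhaustive, but it records changes as slight as dropping the interquartile range. The document history mentions clarified analysis sets, but it compares SAP versions and does not declare a departure from the protocol.

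Three stronger readings are tempting, and the documents do not support them:
- *Pre-dose events might drop out of both columns*, if Day 1 moved to the first commercial dose. SAP section 2.1.1 ties its start-date rules to the randomized arm and to study drug, which the sponsor does not supply to usual care. Day 1 for a crossover is randomization.
- *The arms might have unequal event windows*, because the end dates differ: for inclisiran participants, "Study treatment end date is defined as the treatment phase completion date recorded on the" Treatment Disposition form; for usual care, last contact. Section 2.7.1 does not invoke those dates, and the on-treatment definition covers usual care as well.
- *Crossovers might be higher-risk patients and so create a false signal.* The documents give no ground for a risk difference. Such selection would in any case come from as-treated grouping, not from the missing split.

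**Conclusion.** The point holds as a minor one. SAP section 2.2 with Table 2-1 departs from protocol section 12.1, section 4 does not say so, and the stated rules place pre-exposure events and worst laboratory values under inclisiran.

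The numerical effect is small: with the assumed 2% to 10% crossover, a true risk ratio of 1.85 moves to about 1.84 to 1.81, and about 0.3 to 1.9 participants have a misplaced event of a type with 15% risk. These figures rest on assumed crossover rates, timing and risks. Return to the protocol's grouping would not reduce the dilution. The case for change is correct attribution and disclosure, not the rescue of a distorted result. The primary analyses and the analyses of secondary efficacy variables use the Full Analysis Set as randomized and are not affected.

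**What to change.** 1. List the change of Safety Set grouping in SAP section 4.
2. If the SAP Table 2-1 grouping is kept, count a crossover's treatment-emergent events and worst laboratory values under inclisiran only from the first inclisiran dose, and earlier ones under Usual Care. A split participant appears in both columns, so report that event table per person-time.
3. Add one as-randomized summary of treatment-emergent events, consistent with the protocol, carrying the planned risk ratios.

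The cost is SAP wording, one flag built from event and concomitant-medication dates already collected, person-time for the split table, and a few extra tables. SAP section 5.1.3 does not impute wholly missing medication start dates, so a rule is needed for a crossover whose first dose is undated. The as-randomized table places inclisiran events after crossover under Usual Care, so it supplements the split table and does not replace it. Neither table removes any selection into crossover.
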